## 6. Subject Information

Inclusion criteria:

1. Referral to interventional pulmonology or ENT for endoscopic management of suspected benign tracheal stenosis.
2. Significant tracheal stenosis defined by stenosis  $\geq 50\%$  of tracheal lumen assessed on chest CT or clinical symptomatology warranting evaluation.
3. Able to provide informed consent
4. Age  $> 18$

Exclusion criteria:

1. Inability to provide informed consent.
2. Pregnancy
3. Known or suspected malignant central airway stenosis
4. Patient has already been enrolled in this study.
5. Study subject has any disease or condition that interferes with safe completion of the study including:
  - e. Hypoxemia with need for supplemental oxygen  $\geq 2\text{L/min}$  by nasal canula
  - f. Recent pneumothorax in the previous 12 months
  - g. Severe COPD (defined as a FEV1/FVC  $< 70\%$  and FEV1  $< 30\%$  predicted) and/or severe persistent asthma.
  - h. Hemodynamic instability with systolic blood pressure  $< 90$  mmHg or heart rate  $> 120$  beats/min, unless deemed to be stable with these values by the attending physicians.
6. Prior complications with SCT
7. Contraindication to rigid bronchoscopy
8. Significant tracheomalacia or alterations in cartilage integrity that would require stent placement or surgical referral as assessed by CT imaging.
9. Greater than 1 BCAS intervention within 6 months before enrollment

7. Outcomes

**Primary endpoint:**

The primary endpoint will be the degree of re-stenosis at 6 months expressed as the percentage of airway lumen volume within the stenotic segment at 6 months compared to personal best patency volume on CT scan performed within five weeks of the study intervention. If patients require repeat intervention before six months based on clinical course, a CT chest before this re-intervention will be analyzed for the primary outcome. All analyses will be performed using OsiriX (Pixmeo, Geneva, Switzerland, see below).

**Secondary and exploratory endpoints:**

- **Change in PEF (Secondary)**
- **Change in QOL questionnaire (Secondary)**
- **Incidence of complications between groups (Secondary)**

8. Statistical Design

**8.1: Expected Outcomes**

- We anticipate being able to enroll 40 patients over 1-year period at VUMC with the possibility of opening the study at a second site if enrollment is deemed insufficient at 6 months (15 patients enrolled or less)
- We expect to observe a significant difference in percent change of stenotic volume between SCT-treated patients and controls suggesting decreased recurrence in SCT-treated patients.

**8.2: Randomization**

Patients will be randomly allocated in a 1:1 ratio in permuted blocks of 4 and 6 to intervention or control arms via randomization module in REDCap. Randomization tables will be set up by a study statistician with no role in recruitment, enrollment, or subsequent randomization and will not be available to study personnel performing these tasks.

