## 5. Study Design

### **5.1 : General Study Design**

Subjects will be randomly allocated in a 1:1 fashion to intervention standard of care (SOC) + SCT and control (SOC) groups. Participants will be blinded to the use of SCT to prevent knowledge of their group assignment from biasing their subjective assessments. Adjudicators in the primary outcome measurements (quantitative CT) will be blinded to group assignment as well. Patient will be excluded who have received greater than 1 BCAS intervention within 6 months of enrollment. All operators will be experienced truFreeze users with proper passive venting training as defined by truFreeze protocol. All operators will have a minimum experience of 5 prior procedures.

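### The protocol prints its small block sizes (4 and 6) although operators learn the arms they treat, so the next arm could be guessed up to about 69% of the time; withholding the sizes and loading a less predictable list is a cheap improvement

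*Protocol*

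**What the plan says.** Protocol section 8.2 allocates patients "randomly allocated in a 1:1 ratio in permuted blocks of 4 and 6 to intervention or control arms", "via randomization module in REDCap". It protects the list itself: "Randomization tables will be set up by a study statistician with no role in recruitment, enrollment, or subsequent randomization", and the tables "will not be available to study personnel performing these tasks". No stratification factor is named.

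Section 5.1 blinds two groups: "Participants will be blinded to the use of SCT to prevent knowledge of their group assignment from biasing their subjective assessments", and "Adjudicators in the primary outcome measurements (quantitative CT) will be blinded to group assignment as well". The synopsis adds those who run the statistical analysis. Operators are not listed, and cannot be, because sections 5.1.2 and 5.1.3 have them apply or omit the spray.

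On sites, section 8.1 states: "We anticipate being able to enroll 40 patients over 1-year period at VUMC". A second site is possible if 15 or fewer patients are enrolled at 6 months. The synopsis calls the trial multicentre.

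On entry, section 6 accepts stenosis of at least 50% "assessed on chest CT or clinical symptomatology warranting evaluation". It also lets attending physicians judge whether a patient with out-of-range blood pressure or heart rate is stable.

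**The concern.** Section 8.2 aims at concealment and withholds the tables from recruiting staff, yet the protocol those staff hold discloses the block structure. In a blocked list the arm that is behind is more likely to come next. Anyone who has seen the earlier arms can use this, and small blocks make it work more often. Operators learn the arm of each patient they treat.

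If the same people also influence who is enrolled or when, judgement in the entry criteria gives them room to act on a guess. Patients expected to do better could then drift towards one arm. Blinded CT reading does not remove that bias, because it arises before randomisation. In a trial of 40, a modest drift is visible against the planned difference of 20 points.

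**Working it through.** The protocol gives no guessing rate, so there is no figure of its own on this point to reproduce. Its design figures are used as inputs.

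**Inputs**
- Section 8.2: 1:1 allocation, blocks of 4 and 6. Their order is not stated; random and equally likely is assumed.
- Section 8.3: difference 90 − 70 = 20 points, SD 20, 16 per arm for analysis, 40 enrolled. The normal approximation gives 2 × (1.96 + 0.84)² × (20/20)² = 15.7, so 16 per arm reproduces.
- Two-sided 5% testing is assumed.

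**Step 1. Guessing rate with full sight of earlier arms.** The guesser names the arm that is behind and tosses a coin when the arms are level. In a block of size b the expected number of correct guesses is b/2 + (2^b / C(b, b/2) − 1)/2.
- Block of 4: 2 + (16/6 − 1)/2 = 2.833, and 2.833/4 = 70.8%.
- Block of 6: 3 + (64/20 − 1)/2 = 4.1, and 4.1/6 = 68.3%.
- Equal numbers of both: (2.833 + 4.1)/10 = 69.3%.
- Simulation of 40 patients with sizes in random order: 68.9%.

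**Step 2. What the printed sizes add.** The rule in step 1 does not use the block sizes. A Bayes-optimal guesser who knows them also scores 68.9%. The gain from knowing them is certainty about roughly 6% of assignments.

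**Step 3. Partial sight.** Simulated rates for an operator who sees only his or her own patients:

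| Share of list seen | Names the arm that is behind | Bayes-optimal, sizes known |
|---|---|---|
| One half | 55% | 59% |
| One third | 53% | 56% |
| One quarter | 53% | 55% |

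**Step 4. Bias if guesses are acted on.** Suppose the recruiter picks patients whose outcome would be η points better or worse than average, according to the guess. The bias is then 2 × η × (2p − 1), where p is the guessing rate. No document supports a value of η; 2 and 5 are assumptions.
- Full sight, p = 0.689: η = 2 gives 2 × 2 × 0.378 = 1.5 points; η = 5 gives 2 × 5 × 0.378 = 3.8 points.
- Half sight, p = 0.55 to 0.59, η = 5: 2 × 5 × 0.10 = 1.0 to 2 × 5 × 0.18 = 1.8 points.

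**Step 5. Type I error.** With 16 per arm, SE = 20 × √(2/16) = 7.07.
- η = 2: shift 1.5/7.07 = 0.21 SE; P(Z > 1.75) + P(Z < −2.17) = 5.5%.
- η = 5: shift 3.8/7.07 = 0.53 SE; P(Z > 1.43) + P(Z < −2.49) = 8.3%.

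If all 40 are analysed, SE = 20 × √(2/20) = 6.32 and the two results are 5.7% and 9.2%. Simulating the whole t-test gives biases of about 1.5 to 1.6 and 3.6 to 3.8 points, with errors of about 6% and 8% to 9%.

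**Step 6. Alternatives, full sight, 40 patients.**
- Blocks of 8, 10 and 12 in random order: about 64%. Bias at η = 5 is 2 × 5 × 0.28 = 2.8 points.
- Fair coin with a maximum tolerated imbalance of 3: about 58%. Bias at η = 5 is 2 × 5 × 0.16 = 1.6 points.

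**The case against.** A reader might infer that operators see every assignment on one unstratified list, so that 69% is the actual rate. The documents do not say so. Section 8.2 speaks of tables in the plural, section 5.1 of several operators, section 6 of two referring services, and section 8.1 of a possible second site. Stratification may be set in REDCap or in the statistical analysis plan, which is not at hand. So 69% is an upper bound.

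A reader might also infer that printing the sizes causes the 69%. It does not (step 2). Deleting them from the protocol, with the list unchanged, would leave the average rate where it is.

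Guessing is not steering. Section 8.2 provides central electronic allocation, an independent statistician, withheld tables and two block sizes, and nothing in the protocol shows these failing. The primary endpoint is each patient's 6-month volume relative to his or her own best volume after the procedure. A recruiter would have to foresee relative restenosis, and choosing milder stenoses need not shift that. Accrual of 40 in a year leaves little room to pass patients over. A type I error near 9% therefore cannot be read as what this trial will have. It needs full sight, action on every guess, 5 points of steering and all 40 analysed.

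All of this stands. What remains is that the protocol does not separate those who learn the arms from those who enrol, and that predictability can be lowered at almost no cost.

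**Conclusion.** The point holds as a minor, inexpensive improvement. Mixed permuted blocks with central allocation are a coherent method, and section 8.2 contains no error or contradiction.

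Predictability is at most about 69% with full sight of one unstratified list, and about 53% to 59% when a quarter to a half of it is seen. The printed sizes add certainty for about 6% of assignments.

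The bias is conditional on two things that the documents do not settle: whether those who see assignments also influence enrolment, and how far they could select on the outcome. Under full sight and an assumed 2 to 5 points of steering it is about 1.5 to 3.8 points of the planned 20, with type I error about 6% to 8% at 16 analysed per arm. With half the list seen, even 5 points of steering gives only 1.0 to 1.8 points.

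**What to change.** Delete the block sizes from section 8.2 and say that the allocation details are kept in a restricted randomisation document held by the study statistician. Because the present sizes are already disclosed, load a new, undisclosed and less predictable list into the same REDCap module. Larger, randomly varied blocks (about 64%) or a coin with a maximum tolerated imbalance (about 58%) would both serve; the choice is the statistician's.

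The cost is one protocol sentence and one new table, with no added staff or patients. With a cap of 3 the arms may finish 21 v 19, an effective size per arm of 2 × 21 × 19/40 = 19.95 instead of 20. The cap also forces about 15% of assignments, so it must stay undisclosed: if it were known, more assignments would be certain than the roughly 6% under the present design.

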**8.3: Power Calculation and target accrual**

A search of the literature in idiopathic tracheal stenosis (ITS) shows that clinical recurrence after first intervention can happen as early as 6 months. A study by Perotin et al out of 9 institutions of 23 patients with ITS found recurrence of stenosis to be 30% at 6 months, 59% at 2 years, and 87% at 5 years with a delay of 14 to 16 months. Further a study by Gelbard et al evaluated 603 patients who underwent endobronchial dilation in ITS and found the time to stenosis reoccurrence averaged 1.3 years, which was considerably shorter than cricotracheal resection. We hypothesize that the earliest signs of loss of airway patency will be evident at 6 months by radiologic CT-based volumetric assessment, which will detect early (as opposed to clinical) recurrence. Our results will inform the design of future larger studies.

We hypothesize the patency assessed at 6 months will be 90% of baseline in the intervention group and 70% in the control group, with SD 20% in the control group. The sample size estimation was completed using two-sample t-test. For the pilot study, a sample size of 16 subjects in control and 16 subjects in intervention group will have 80% power to detect an increase in stenotic volume of 20% from control arm with type I error of 0.05. An additional 8 patients will be enrolled (attrition), for a total target accrual of 40 patients. Likert scale will be used after treatment to determine the minimal clinically important difference for future studies using this endpoint.

**8.4: Analytical Plan**

Descriptive statistics including means, standard deviations, and ranges for continuous parameters, as well as percentages and frequencies for categorical parameters will be presented. Investigations for outliers and assumptions for statistical analysis, e.g., normality and homoscedasticity will be made. If necessary, data will be transformed using Box-Cox power transformation. Comparisons between groups, i.e. intervention vs control, will be made using either the t-test or Wilcoxon Rank Sum test for continuous variables (such as patency volume, visual analog scales) and Chi-square test for categorical variables (such as incidences of pneumothorax). Other than the primary end point of percentage change of patency volume at 6 month, we will apply linear regression to assess the 6-month patency volume difference between control and intervention groups with the adjustment of baseline patency volume. Patients will be analyzed according to the per protocol and intention to treat principle. For peak flows, COPD questionnaire, intermediary time points will be analyzed using mixed model analysis for repeated continuous variables starting from 2 weeks pre-procedure, 3 months and then to 6 months post procedure.

### **8.5 Measurements:**

PEF, quality of life using the Clinical COPD CCQ. Incidence of complications (hypoxemia, bleeding, pneumothorax rate, barotrauma). Baseline characteristics (age, sex, body mass index (BMI), smoking status, underlying disease process). CT Chest without contrast with 3D quantitative reconstruction.

**Peak expiratory flow monitoring:** Evidence supports the use of PEF as a simple, efficient, and accessible way of monitoring progression of tracheal stenosis. PEF has previously been captured in clinical encounters as component of the decision-making algorithm for surgical intervention in tracheal stenosis patients. Mobile Device Software ‘App’ can robustly capture longitudinal patient reported outcome measures..

**CQS mobile computing group:** Established expert programmer and data scientist support dedicated to mobile application development and support. Prior work with the CQS team successfully created and deployed a mobile app (Airflo™) for tracheal stenosis patient PEF reporting. Leveraging a Research Electronic Data Capture (REDCap) foundation, mobile apps are built on open-source mobile computing "MyCap" infrastructure (<https://projectmycap.org/>). MyCap leverages REDCap, ResearchKit (Apple: iOS), and ResearchStack (Android) to capture patient reported outcome measures, and physiologic tasks (such as maximum phonation time, voice samples, and peak expiratory flow rate) using iOS and Android mobile devices. REDCap is used to define tasks/instruments/surveys to be completed by participants. MyCap translates REDCap task metadata into a structure compatible with ResearchKit and ResearchStack. When a project participant completes a task, MyCap converts the results into a format compatible with REDCap before synchronizing back to the REDCap project.

## **9. Outcome Measure Synopsis**

### **9.1: Quantitative imaging of stenotic volume**

Airway segmentation and measurement of the patency volume will be performed as follows by two experienced operators ([name]). DICOM images of CT scans will be transferred to the LungCloud™ platform.

The LungCloud™ is provided by Neurotargeting LLC, a spin-off of Vanderbilt University. The LungCloud™ is a health IT clinically approved system for the collection of complete data sets in the clinical flow, including but not limited to clinical outcome, radiology notes and scans. The LungCloud™ is set up as a network of accounts that can be interconnected around a clinical study. The managing institution creates a Clinical Trial inside the LungCloud™ and ties it to each of the institutions. Each institution is then able to collect and share data for the clinical study. Data is collected in the clinical flow and from PACS and stays at all time in the LungCloud™ instance of the institution owning the data.

Image data is encrypted and sent to the institution's LungCloud™. Automatic uploading of images is achieved through what is referred to as the LungDrive. This is a process that runs on the end user's machine and works in a way similar to Box or Dropbox, i.e., any new image volume placed in a specific folder is automatically encrypted and uploaded to the account repository. The non-imaging data can be entered into the system and associated with the imaging data through web-based forms customized to the end users. Images are reconstructed in 3D and can be reviewed in any view (sagittal, coronal or axial). The system offers a series of web-based user interfaces that permit inspecting and visualizing both imaging and non-imaging data.

Deanonimized DICOM images will be transferred and analyzed using the OsiriX (Pixmeo, Geneva, Switzerland) threshold-based region growing algorithm function for volume segmentation. Briefly, the process is as follows: The operator identifies proximal and distal ends of the tracheal stenotic and use the region of interest (ROI) function to segment the trachea in 3 to 4 different areas spanning the length of the stenotic segment using the closed polygonal function (Figure 5). The ROI volume function will then be used to generate missing intervening ROIs and the repulsor function will be used to manually adjust the boundaries of the ROI. The volume of the final airway will then be computed and a three-dimensional image saved for documentation (Figure 6).

To classify the degree of tracheal stenosis, we will manually annotate the trachea (wall, stenosis, and patency) on all scans. Expert manual review will be performed by one of two experienced investigators ([name]) In an exploratory analysis to enable routine automated analysis of stenotic volumes, we will perform transfer learning using our abdomen/thoracic model using leave-one-out cross-validation. Mixture modeling with image intensity classification will be used to separate the tracheal wall, stenosis region, and patency following our work in the abdomen.

[figure not shown]

Figure 5. Closed polygonal function-derived 2D-tracheal segmentation

[figure not shown]

Figure 6. 3D reconstruction and computation of the patency volume

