#### **5.1.4 : Both groups**

Peak expiratory flow (PEF) as well as a quality of life (QOL) questionnaires will be obtained within 2 weeks before and 2 weeks after the procedure. A repeat thin-cut chest CT or neck to quantitatively estimate of the patency volume will be obtained within 5 weeks of the first procedure to establish personal best patency volume (baseline patency volume, see below). A final CT scan will be done at 6 months after the index study procedure to evaluate the degree of restenosis. A QOL questionnaire and check-in survey will be done at the at the 3-month. Patients will have a final QOL questionnaire at the 6-month mark. Patients will be doing continuous PEF measurements weekly throughout the study with a mobile application as mentioned below.

Throughout the follow up period if a patient meets one or both of the following criteria: 1) drop in peak flow to 30% of previous value 2) drop in dyspnea score by 30% then the investigators will review if the patient needs an early CT and possibly repeat bronchoscopy. If patients undergo a repeat procedure before the 6-month CT they will be analyzed in an early reintervention subgroup. These patients will be including in the final analysis as per intention-to-treat and thereafter followed as per follow-up procedures outlined in the protocol. Patients in the SCT group may get repeat SCT as per discretion of the proceduralist. Patients in the SOC will not be able to get SCT and may only have repeat dilation with laser radial cuts.

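### Nothing requires the primary CT volume ratio to cover the same stretch of trachea on both scans, so a longer re-stenosis can score as better patency

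*Protocol*

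**What the plan says.** Section 7 of the protocol defines the primary endpoint as "the percentage of airway lumen volume within the stenotic segment at 6 months compared to personal best patency volume". A higher value means better patency. The denominator is a CT taken after the study procedure. The numerator is the 6-month CT, or a CT before re-intervention if that comes first.

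Section 9.1 holds the only measurement procedure. The limits are set by the reader: "The operator identifies proximal and distal ends of the tracheal stenotic and use the region of interest (ROI) function to segment the trachea". The outlines are drawn "spanning the length of the stenotic segment using the closed polygonal function", missing outlines are interpolated and adjusted by hand, and then "The volume of the final airway will then be computed". The section names no anatomical landmark, no fixed length, no transfer of limits from one scan to the other, and no division by length.

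Section 5.1 blinds the CT adjudicators to arm. Section 8.4 adds a regression of 6-month volume adjusted for baseline volume. Section 8.3 assumes 90% of baseline with SCT and 70% in control, with an SD of 20%.

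**The concern.** A ratio of two lumen volumes measures patency only if both cover the same length of airway. Otherwise it mixes how narrow the airway is with how much of it was outlined.

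The denominator scan follows treatment, so the limits have to be found on an airway that has just been opened. A pre-treatment scan showing the original stenosis is not guaranteed. Inclusion criterion 2 in section 6 allows entry on symptoms, and the assessment table in section 20 lists CT only after the procedure and at 6 months.

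At stake is the score given to individual patients on the primary endpoint, and the power of a comparison planned with 16 evaluable patients per arm. Section 8.3 also intends the results to inform larger studies, so a weakness in the measure would carry forward.

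**Working it through.** **1. The plan's own figure.** Inputs from section 8.3: difference 90 − 70 = 20 points, SD 20, type I error 0.05, power 80%. I take the test as two-sided and the SD as common to both arms. The normal approximation gives 16 per arm, with 80.7% power at 16. The t-test gives 16.7 per arm and 78.1% power at 16. The plan's 16 per arm is reproduced to within rounding of method and is not in dispute.

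**2. Structure of the endpoint.** Volume = mean lumen area × length, so

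volume ratio = (area at 6 months / area at baseline) × (length at 6 months / length at baseline).

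With one common segment the length ratio is 1 and the score is the area ratio: 70% stays 70%, and 90% stays 90%.

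**3. Effect on one patient.** The length ratios below are assumptions, because the protocol gives none. The area ratio is held fixed.

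| True area ratio | Length ratio | Score |
|---|---|---|
| 70% | 0.75 | 52.5% |
| 70% | 1.00 | 70% |
| 70% | 1.10 | 77% |
| 70% | 1.29 | about 90% |
| 70% | 1.50 | 105% |
| 50% | 1.50 | 75% |
| 50% | 2.00 | 100% |

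The hypothesised control value becomes the hypothesised SCT value at 0.90 / 0.70 = 1.286, that is, 29% longer. It reads as no re-stenosis at 1 / 0.70 = 1.43.

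**4. Effect on the comparison, three cases.**

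*Same length ratio in everyone.* At 1.1 the means become 77 and 99, the difference 22, and the SD 20 × 1.1 = 22. The standardised difference is still 22 / 22 = 1, so power does not change.

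*Random picking error only.* Let each length have coefficient of variation c, independently on the two scans, and let the mean score be 80. Then approximately

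SD² = 20² × (1 + 2c²) + 80² × 2c².

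For c = 10%: 400 × 1.02 + 6400 × 0.02 = 408 + 128 = 536, so SD = 23.2.

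| c | SD | t-test power at 16 per arm |
|---|---|---|
| 0 | 20 | 78% |
| 5% | 20.8 | 75% |
| 10% | 23.2 | 66% |
| 20% | 30.7 | 43% |

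*Lengthening in the control arm only, SD kept at 20.* Difference = 90 − 70 × length ratio. At 1.1 it is 13 points (power about 45%, normal approximation). At 1.2 it is 6 points (about 13%). At 1.286 it is 0. This shows sensitivity and is not a forecast.

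**5. Do existing safeguards remove it?** Blinding to arm does not fix the length. Adjusting 6-month volume for baseline volume does not either, because the length drawn at 6 months still enters the outcome.

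**The case against.** The strongest reply is that the protocol never says the limits are picked anew on each scan. The endpoint refers to the stenotic segment in the singular, which can mean one common segment, and on that reading the bias disappears. Section 9.1 also calls its description brief, its figures are not available here, and a reading manual may hold the rule. This stands as far as it goes: re-picking is an inference, and the point must be stated conditionally. It does not dispose of the point, because the protocol spells out the measurement step by step and the one step that decides the result is left to the reader. Followed literally, that step can produce a wrong primary value.

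Several stronger readings are tempting, and the documents do not support them:

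- *A longer re-stenosis always scores better.* It does so only if the limits are re-picked and the extra length outweighs any further narrowing. A shorter pick lowers the score.
- *The result is biased towards one arm.* Readers are blinded to arm, and nothing in the documents shows that length changes differ between arms. Without such a difference the effect is mainly noise.
- *The SD of 20% omits this noise.* Section 8.3 gives no source or components for that SD, so this cannot be known. The SD table in the working shows what follows if it does.
- *Each scan is measured by only one of two readers.* The sentence "Expert manual review will be performed by one of two experienced investigators" belongs to the classification of stenosis. For the volume itself, section 9.1 names two experienced operators, without saying whether both measure every scan or share them.
- *Chest or neck coverage distorts the ratio.* Section 5.1.4 allows "A repeat thin-cut chest CT or neck to quantitatively estimate of the patency volume", but coverage does not change the volume of a segment visible on both scans.
- *The images unblind the readers.* "Deanonimized DICOM images will be transferred and analyzed" is at most a wording slip. Identity on an image is not knowledge of allocation.

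**Conclusion.** The point holds in conditional form. The protocol combines a reader-chosen segment, an un-normalised volume and no rule tying the two scans together. If the limits are re-picked, the primary ratio is area ratio times length ratio. A 10% length mismatch then moves a true 70% by 7 points, which is 35% of the 20-point target (7 / 20), and a 29% mismatch covers the whole target. Non-differential error biases neither arm in particular but can cost material power, to about 66% at an assumed 10% variation in each length.

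All these sizes rest on assumed length ratios or variation and on a fixed area ratio. If one common segment is used, none of them arises. The change should be made, because the primary endpoint depends on it and the cost is small. The sample size does not need to change on this account: with a length ratio of 1 the planned difference and 16 per arm stand as they are.

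**What to change.** State in section 9.1, and refer to it from section 7:

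1. The segment is defined once per patient by distances from a fixed landmark such as the carina or the vocal folds. Use whichever available scan shows the stenosis or, if none does, the treated segment as located at the index bronchoscopy.
2. The same ends and length are applied to every scan of that patient: personal-best, 6-month and pre-reintervention.
3. Mean lumen area (volume divided by length) is reported alongside the volume ratio.
4. The same existing reader or readers measure all scans of a patient, masked to arm and to scan date.

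Separately, correct the word describing the images to de-identified, if that is what is meant.

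The cost is some reading-manual wording and the work of matching landmarks between scans. No additional scan or reader is needed. One limit should be acknowledged: narrowing that extends beyond the fixed ends is not counted, so any such extension should be recorded descriptively.
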